5 STUDY ENTRY AND WITHDRAWAL PROCEDURES

5.1 Registration Procedures

To register a patient, the study team will provide the following to the registrar at VCU Massey Cancer Center [REDACTED]

- Registration cover sheet
- Completed eligibility checklist
- Signed & dated informed consent form

The registrar will complete the registration process by assigning a study ID number and forwarding the “Confirmation of Registration” form to the registering study team.

No patient may begin study treatment until the Confirmation of Registration assigning a study ID number has been received from the registrar. The registering study team will enter into the OnCore database the patient’s initial enrollment data (demographics, consent, eligibility, on study, treatment assignment) within 24 hours of registration and before treatment begins.

5.2 Study Discontinuation Procedures

5.2.1 A patient may decide to withdraw from study participation at any time.

5.2.2 Patients will be removed from study treatment and enter into the follow-up phase when any of the criteria listed in Section [7.6](#) “Duration of Therapy” applies.

5.2.3 A patient may be removed from the study follow-up phase and be taken off study for any of the following reasons:

- Investigator determination that discontinuation is in a patient’s best medical interest
- Withdrawal of support of study sponsor

- 5.2.4 The reason for study removal and the date the patient was removed must be documented in the source documents and the OnCore case report forms (CRFs).

6 TREATMENT PLAN

6.1 Baseline Tests and Procedures

Refer to Section [12](#), Study Calendar, for the screening tests and procedures that are required prior to treatment and/or registration, and for the timing of these events relative to the start of combination treatment.

6.2 Schedule

The treatment schedule is combined sorafenib, valproic acid, and sildenafil, administered orally, twice daily continuously. A cycle consists of 4 weeks. The first cycle begins once therapy begins with all 3 agents—after, if necessary, titration of valproic acid dosage, described in Section [6.2.7](#). Titration of valproic acid may occur as a matter of clinical preference, prior to study enrollment.

Study drug therapy is taken on an empty stomach, that is, at least 1 hour before or 2 hours after eating, due to absorption characteristics of sorafenib.

The first 6 patients evaluable for qualifying toxicity assessment will be treated as a safety lead-in; enrollment will be gated (the first 3 evaluable patients must complete 4 weeks of the combination therapy before the next 3 patients start combination treatment on protocol) and patients will undergo weekly evaluations for qualifying toxicities (Section [6.4.2](#)) during the first 4 weeks of combination therapy.

- 6.2.1 Initiation of sorafenib and sildenafil will not take place until valproic acid levels are \geq LLN for the laboratory, which generally takes 5-7 days after initiation.
- 6.2.2 Valproic acid will be administered orally, generally twice daily. The tablets or capsules should be swallowed without chewing to avoid local irritation of the mouth and throat. Patients who experience gastrointestinal irritation may benefit from administration of the drug with food or by slowly building up the dose from an initial low level.
- 6.2.3 If a patient is already on valproic acid and blood levels are \geq LLN for the laboratory, no further titration is necessary.
- 6.2.4 If a patient presents for evaluation for this study and are at risk for seizures, the patient may be started on valproic acid.
- 6.2.5 If a patient is already on non-valproic acid antiepileptic therapy, they may be transitioned to valproic acid, as a matter of clinical preference, prior to enrollment to obtain levels \geq LLN for the laboratory prior to discontinuing the original antiepileptic therapy.
- 6.2.6 Patients with disease recurrence require routine maintenance on antiepileptic therapy. If a patient presents for study evaluation before initiation of antiepileptic

medication, patient may start valproic acid titration to \geq LLN for the laboratory as a matter of clinical care.

- 6.2.7 Valproic acid titration: Titration to levels \geq LLN for the laboratory generally takes 5-7 days. The FDA recommends that valproic acid doses start at 10-15 mg/kg/day. If a patient is already on a stable dose of valproic acid, the drug does not need to be titrated unless the dose is less than the LLN.
- 6.2.8 Sorafenib is dosed at 400 mg orally, twice daily, continuously. Subsequent dose modifications are allowed based on toxicity assessment.
- 6.2.9 Sildenafil is dosed at 50 mg orally, twice daily, continuously. Subsequent dose modifications are allowed based on toxicity assessment.

6.3 Radiographic Evaluations

- 6.3.1 MRI of the brain obtained within 3 weeks prior to entry into the protocol can be used as baseline staging evaluation. In the event that MRI scans cannot be performed, contrast-enhanced CT scans can be used. If scans were obtained from another institution, copies should be obtained and maintained in the research files.
- 6.3.2 A reasonable dose of corticosteroids will be determined on clinical grounds for each patient. An effort will be made to keep the patient on this steroid dose for at least 5 days prior to the next MRI or contrast-enhanced CT scan. If it is not possible to keep the steroid dose constant for 5 days then the MRI scan will be delayed until the dose has been stable for 5 days.

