10.2.1 Neurologic Exam Status

Table 12. Neurologic Exam Status as Compared to Pre-Treatment Exam

Status	Criteria
Better	No new neurologic deficits. Must be on stable or decreasing dose of steroids, with stable to improved ECOG performance status
Worse	New neurologic deficits, declining ECOG performance status, or requiring increasing dose of steroids to remain stable

10.2.2 MRI Assessment: Based on Response Assessment in Neuro-Oncology working group (RANO) criteria [\(37\)](#).

Table 13. RANO Criteria

Response	Criteria
Complete Response	Requires all of the following: Complete disappearance of all enhancing measurable and non-measurable disease sustained for at least 4 weeks; no new lesions; stable or improved non-enhancing (T2/FLAIR) lesions; and with patient off corticosteroids or only on physiological replacement doses. Requires repeat MRI in 4 weeks for confirmation.
Partial Response	Requires all of the following: $\geq 50\%$ decrease, compared with baseline, in the sum of products of perpendicular diameters of all measurable enhancing lesions sustained for at least 4 weeks; no progression of non-measurable disease; no new lesions; stable or improved non-enhancing (T2/FLAIR) lesions on the same or lower dose of corticosteroids compared to baseline scan; and with patient on a dose corticosteroids not greater the dose at the time of baseline scan, and is stable or doing better clinically. Requires repeat MRI in 4 weeks for confirmation.
Stable Disease	Stable disease occurs if the patient does not qualify for complete response, partial response, or progression, and requires the following: Stable non-enhancing (T2/FLAIR) lesions on the same or lower dose of corticosteroids compared with baseline scan and clinically stable status. In the event that the corticosteroid dose was increased for new symptoms and signs without confirmation of disease progression on neuroimaging, and subsequent follow-up imaging shows that this increase in corticosteroids was required because of disease progression, the last scan considered to show stable disease will be the scan obtained when the corticosteroid dose was equivalent to the baseline dose.

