Progressive Disease	Progression is defined as any of the following: $\geq 25\%$ increase in the sum of the products of perpendicular diameters of enhancing lesions, on stable or increasing doses of steroids; a significant increase in non-enhancing (T2/FLAIR) on stable or increasing dose of steroids compared with baseline scan or best response after initiation of therapy; the appearance of new lesions; clear progression of non-measurable lesions; definite clinical deterioration not attributable to other causes apart from tumor or to decreases in corticosteroid dose.

10.2.3 Contrast-enhanced CT Assessment: Based on Macdonald Criteria (38).

Table 14. Macdonald Criteria

Response	Criteria
Complete Response	Requires all of the following: complete disappearance of all enhancing measurable and non-measurable disease sustained for at least 4 weeks; no new lesions; no corticosteroids; and stable or improved clinically.
Partial Response	Requires all of the following: $\geq 50\%$ decrease compared with baseline in the sum of products of perpendicular diameters of all measurable enhancing lesions sustained for at least 4 weeks; no new lesions; stable or reduced corticosteroid dose; and stable or improved clinically.
Stable Disease	Requires all of the following: does not qualify for complete response, partial response, or progression; and stable clinically.
Progression	Defined by any of the following: $\geq 25\%$ increase in sum of the products of perpendicular diameters of enhancing lesions; any new lesion; or clinical deterioration.

*Table from (37)

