10.4 Timing of Imaging Studies

For the purposes of this study, patients will be re-evaluated for response every 8 weeks. In addition to a baseline scan, confirmatory scans should also be obtained 4 weeks following initial documentation of objective response (PR or CR).

Evaluation of neurologic imaging can be confounded by factors such as edema and subtle variances in imaging parameters. In the event that imaging meets objective progression criteria, but the patient's clinical status is stable or improving, with a stable or decreasing steroid dose, and, in the opinion of the investigator, the aggregate patient assessment is not definitive for progression, study therapy can continue at investigator's discretion with repeat imaging at time of next scheduled assessment. If subsequent imaging again meets objective progression criteria, regardless of clinical and/or steroid dosing status, then progression criteria will have been met, and the date of progression will be noted as the earliest imaging date that was consistent with objective progression.

If clinical conditions raise the concern for progressive disease in between regularly scheduled interval scans, repeat imaging may be performed at the treating physician's discretion.

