13.2 Sample Size/Accrual Rates

The sample size and power are calculated based on Simon's two-stage mini-max design which minimizes the expected maximum sample size ([35](#)). The primary outcome, 6-month PFS, is considered as a binary variable, ie, a patient either has 6-month PFS or not. Per the previous studies of second-line therapy in GBM, we assume that the null hypothesis, the proportion of patients who have 6-month PFS, is $\leq 20\%$, ie, $p_0 \leq 0.2$, which is unacceptably low, and the true proportion is $p_1 = 0.4$. With a one-sided type I error of 5% and power of at least 80%, the first stage will enroll 16 response-evaluable patients. If there are 3 or less response-evaluable patients who have 6-month PFS, then the trial in the unselected patient population will end. If 4 or more response-evaluable patients have 6-month PFS, then the trial will enroll an additional 17 response-evaluable patients into the second stage. If 11 or more out of the total of 33 response-evaluable patients have 6-

month PFS, the drug combination meets efficacy criteria and further studies can be pursued.

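### Section 6.3.2 delays scans while the steroid dose is changing, with no maximum and no dating rule, so some worsening patients can be counted as progression-free at 6 months

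*Combined protocol and SAP*

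**What the plan says.** Section 6.3.2 first sets an aim: "An effort will be made to keep the patient on this steroid dose for at least 5 days prior to the next MRI". The same aim covers CT. If that is not possible, the rule becomes mandatory: "then the MRI scan will be delayed until the dose has been stable for 5 days". It states no maximum delay, makes no distinction by direction of dose change, and gives no rule for dating what the late scan shows.

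Other parts of the protocol bear on this:

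- **Table 13 (RANO)** allows radiographic progression to be called on an "increase in the sum of the products of perpendicular diameters of enhancing lesions, on stable or increasing doses of steroids". It also counts definite clinical deterioration as progression, with no scan needed.
- **Table 14 (Macdonald)** counts clinical deterioration as progression.
- **Table 12** scores a patient "requiring increasing dose of steroids to remain stable" as neurologically worse.
- **Section 3.2** defines the primary event as RANO or Macdonald progression, or death. **Section 10.4.2** also names symptomatic progression.
- **Section 10.4** says "patients will be re-evaluated for response every 8 weeks". **Study Calendar footnote J** says every 2 months.
- **Study Calendar footnote B** sets a window of plus or minus 3 days from cycle 3. It can be widened after cycle 2 with prior notice to the principal investigator or designee.
- **Section 13.2** tests 6-month PFS as a yes/no outcome in a two-stage design.

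**The concern.** The delay is related to the outcome. A common reason for an unsettled steroid dose is that the patient is getting worse, and Table 12 itself treats a needed increase as worsening. For that patient Table 13 does not require a stable dose before growth is called progression, so the hold postpones a scan that the protocol's own criteria could already read.

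If the progression date is simply the date of the late scan, the shift is towards later progression. In a single-arm trial judged against a fixed 20%, no control arm offsets such a shift. At stake are the false-positive rate of the go/no-go rule and, to a lesser extent, the median time to progression.

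**Working it through.** **1. The plan's own design.** Inputs from Section 13.2: null proportion 0.20, alternative 0.40, one-sided 5%, power at least 80%. Continue with at least 4 of 16; succeed with at least 11 of 33.

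P(success) = sum over x = 4 to 16 of P(X1 = x) × P(X2 ≥ 11 − x), with X1 ~ Bin(16, p) and X2 ~ Bin(17, p).

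- p = 0.20: 0.0475 (chance of passing stage 1: 0.402)
- p = 0.40: 0.811

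The stated error rates are reproduced.

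**2. Can a hold cross the landmark?** Six months = 365.25 / 2 = 182.6 days.

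*8-week schedule (Section 10.4).* Scans fall on days 56, 112 and 168. The gap to the landmark is 182.6 − 168 = 14.6 days.

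- One dose change just before day 168 moves the scan to about 168 + 5 = day 173. It does not cross.
- To reach day 183, the last dose change must come on about 183 − 5 = day 178 or later, 10 days after the scan was due. That means repeated changes.
- The earlier scans are not a realistic route. Against 26 weeks, the week-8 scan would have to slip 18 weeks and the week-16 scan 10 weeks.
- Footnote B, if it covers imaging and is not waived, allows the scan no later than 168 + 3 = day 171. A full 5-day hold can already break it.

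*2-month schedule (footnote J).* The third scan is due at month 6, on the landmark. Any hold moves it past.

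**3. Which patients are exposed?** Those on rising steroids who are scored worse under Table 12 but not judged to have definite clinical deterioration under Table 13. No section makes a steroid increase alone a progression event. The stable-disease row of Table 13 moves back the last stable scan in this situation but assigns no progression date. Section 10.4 dates progression back only to an earlier scan that already met the criteria, so it does not help when the scan was postponed.

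**4. Sensitivity of the decision rule.** Let f be the share of true 6-month failures counted as successes. Then p_obs = 0.20 + 0.80 f. The documents give no value for f, so the range below is an assumption.

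| f | Observed rate | Extra successes in 33 (33 × 0.80 f) | P(pass stage 1) | P(success) |
|---|---|---|---|---|
| 0 | 20.0% | 0 | 0.402 | 0.0475 |
| 1% | 20.8% | 0.26 | 0.434 | 0.061 |
| 2% | 21.6% | 0.53 | 0.466 | 0.076 |
| 2.5% | 22.0% | 0.66 | 0.481 | 0.085 |
| 5% | 24.0% | 1.32 | 0.558 | 0.138 |

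One patient is 1/33 = 3 percentage points.

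**The case against.** The strongest reply is that a deteriorating patient does not need a scan to progress. RANO and Macdonald both count clinical deterioration, Section 10.4.2 counts symptomatic progression, and Section 10.4 allows imaging between scheduled scans when there is concern. This stands for most patients who are plainly failing. A reader might infer that everyone whose steroids are raised gets a later progression date, and the documents do not support that. What remains is the patient held stable by more steroids, for whom unscheduled imaging is optional and Section 6.3.2 makes no exception.

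A second reply is that footnote B already limits timing. A reader might infer that the protocol has no limit anywhere, and that is also too strong: the absence is in Section 6.3.2. But footnote B can be relaxed, does not mention the steroid hold, and conflicts with a mandatory delay, so the two must be reconciled.

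Third, a single dose change does not cross the landmark on the 8-week schedule. That is correct. On the 2-month schedule any hold crosses, but so would the ordinary 3-day allowance, which shows that the 6-month assessment also needs a stated window.

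Finally, simply ordering scans while steroids are rising may not help. Steroids can soften enhancement, and progression missed that way waits for the next scan, again in the regimen's favour. This stands, and that change should not be the core of the fix.

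**Conclusion.** The gap is real but narrow. As written, Section 6.3.2 can move a progression date past 6 months for patients on rising steroids without definite clinical deterioration. On the 8-week schedule this needs repeated changes that delay the day-168 scan by more than about 2 weeks; on the 2-month schedule any hold is enough.

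How often this would happen cannot be derived from the documents. The rise in false-positive rate from 4.75% to 8.5% rests on an assumed 2-point shift in the observed rate, about 0.7 of a patient in 33. It shows how sensitive the rule is and does not forecast the bias. A reader might take the larger values in the table as expected inflation; nothing in the documents supports a particular value. The point is worth correcting because the primary decision turns on very few patients and the correction is cheap.

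**What to change.** 1. **Dating for the 6-month endpoint (Sections 3.2 and 13.4).** Assign the result of a steroid-delayed scan to its scheduled assessment, so that progression on a delayed 6-month scan counts as a 6-month failure. Report the analysis by actual scan date as a sensitivity analysis.
2. **Delay limit (Section 6.3.2).** State a maximum scan delay. Reconcile it with the plus or minus 3 days in footnote B, and with Table 13, which does not need a stable dose to call progression when the dose is rising.
3. **Schedule and window.** Reconcile the 8-week interval in Section 10.4 with the 2-month interval in footnote J, and state the window within which a scan counts as the 6-month assessment.

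The cost is wording. The sample size stays at 33 per two-stage design and no scans are added. The downside is that some progression dates will fall slightly before the image that showed them, so 6-month PFS may look slightly less favourable.

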6.4 Toxicity Assessments

6.4.1 Toxicity Grading

Adverse events (AEs) will be characterized and graded according to NCI CTCAE version 4.0. See Section [8](#).

6.4.2 Qualifying Toxicities for the Safety Lead-In and Safety Stopping Rule

Qualifying toxicities for the safety lead-in are evaluated weekly during the first 4 weeks of combination treatment for each of the first 6 patients deemed evaluable for qualifying toxicity for the safety lead-in (see Section [10.1](#)).

Qualifying toxicities for the safety stopping rule are evaluated regularly during the first 4-week cycle of combination treatment for patients deemed evaluable for the early stopping rule (see Section [10.1](#)).

Qualifying toxicities are defined as any of the following that are possibly, probably, or definitely related to drug therapy:

Any grade \geq 3 toxicity, except the following:

- nausea, vomiting, or diarrhea in the absence of adequate prophylaxis and/or responsive to medical management
- grade 3 thromboembolic event

- grade 3 hyperglycemia
- grade 3 PPE (hand-foot syndrome)
- fatigue responsive to medical management
- grade 3 hypertension
- electrolyte abnormalities that, once corrected, can be maintained with oral repletion
- grade 3 anemia, platelets, neutrophils, WBC, lymphocytes, febrile neutropenia

6.4.3 See Section [8.5](#) for AE and qualifying toxicity reporting procedures.

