7.1.1 Sorafenib Dose Modifications

Table 1. Sorafenib Dose Modifications

Toxicity		Sorafenib Modification
Cardiac		
Grade \geq 2 acute coronary syndrome (myocardial ischemia) or Grade \geq 2 myocardial infarction		Discontinue sorafenib permanently.
Heart failure	Grade 3	
 Interrupt until \leq grade 1; upon resumption, decrease by 1 dose level. If no recovery after 30 day interruption, discontinue sorafenib permanently unless patient is deriving clinical benefit; confer with PI.
	Grade 4	Discontinue sorafenib permanently.
Skin and Subcutaneous Disorders		
Palmar-plantar erythrodysesthesia syndrome (PPE) (hand-foot syndrome)		See Table 2 'Sorafenib Dose Reduction Guidelines for PPE (Hand-Foot Syndrome).'
Grade 2 rash acneiform		At investigator's discretion, consider holding and/or reducing sorafenib to the next lower dose.
Grade 3 or grade 4 rash acneiform		Hold sorafenib. 
 Re-evaluate at least weekly until resolution to \leq grade 1 or tolerable grade 2. Re-start sorafenib at one dose reduction. If toxicity persists > 14 days, discontinue sorafenib. Patients with grade 4 acneiform rash related to sorafenib may be taken off sorafenib at investigator's discretion.
Stevens-Johnson syndrome or toxic epidermal necrolysis		Discontinue sorafenib if Stevens-Johnson Syndrome or toxic epidermal necrolysis are suspected.
Gastrointestinal Disorders		
Perforation (esophageal, gastric, colonic, duodenal, ileal, jejunal, rectal, or small intestine)		Discontinue sorafenib permanently.

Investigations	

Grade \geq 3 ALT increase in the absence of another cause or
 
AST or ALT $>$3x ULN with bilirubin $>$2xULN in the absence of another cause; or
 
Grade \geq 1 Alkaline phosphatase in the absence of known bone pathology with grade \geq grade 2 bilirubin increase; or
 
any 1 of the following INR \geq 1.5, ascites and/or encephalopathy in the absence of underlying cirrhosis or other organ failure related to drug-induced liver injury
	
Discontinue sorafenib permanently.

Lab abnormalities - not clinically significant
 
Note: For clinically significant lab abnormalities follow the dose modification guidelines for "All Other Non-Hematologic Toxicities."
	
Continue sorafenib and institute supportive measures. At investigator's discretion, consider holding and/or reducing sorafenib to the next lower dose.

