Grade 3 electrocardiogram QT corrected interval prolonged	
See also Section 7.4.8
 
Hold sorafenib
 
 • Check and immediately administer potassium to achieve levels of ≥ 4 and magnesium to levels of ≥ 2. • Consider chronic oral supplementation of potassium and/or magnesium. • Review with principal investigator prior to patient's next scheduled treatment, considering the following options: 
 ○ STOP sorafenib until QTc recovers to pre-study treatment baseline (grade 1 or less, or ≤ 480ms). ○ When QTc returns to baseline, reinstitute sorafenib cautiously, with additional QTc monitoring at earliest possible follow-up opportunity, but no more than 8 days from reintroduction of sorafenib. ○ If QTc prolongation event felt attributable to sorafenib, reduce sorafenib to the next lower dose. • For recurrent QTc grade 3 felt attributable to sorafenib despite dose reduction, consider permanent discontinuation of sorafenib.
Grade 4 electrocardiogram QT corrected interval prolonged	Discontinue sorafenib. Do not restart.
Nervous System Disorders (potentially reflective of cardio-toxicity)	
Grade 2 pre-syncope or grade 3 syncope	
See also Section 7.4.8
 
 • Obtain ECG for cardiology review/consultation. • Check and immediately administer potassium to achieve level of ≥ 4 and magnesium to level ≥ 2. • If ECG shows new dysrhythmia or QTc \geq grade 2 (> 480ms), hospitalize for monitoring with Cardiology consultation. • STOP sorafenib until any potassium and magnesium abnormalities are corrected, symptoms resolved and QTc returns to grade 1 or less (≤ 480ms). • Reintroduce sorafenib cautiously, with input from Cardiology and with additional QTc evaluation, either concurrent with reintroduction or at earliest possible follow-up opportunity and no more than 8 days from reintroduction. • If event felt attributable to sorafenib, reduce sorafenib to the next lower dose. • Consider chronic oral supplementation of potassium and/or magnesium. • For recurrent syncope or near-syncope felt attributable to sorafenib, consider permanent discontinuation of sorafenib.
Vascular Disorders	
Hypertension	See Table 3 'Management of Hypertension.'
All Other Non-Hematologic Toxicities	
Grade ≥ 2 hemorrhage (requiring medical intervention)	Discontinue sorafenib permanently.

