10 MEASUREMENT OF EFFECT

10.1 Definitions

Evaluable for toxicity. All patients will be evaluable for toxicity from the time of their first treatment with sorafenib and/or valproic acid and/or sildenafil.

Evaluable for qualifying toxicities for the safety lead-in. Only those patients who have completed the first cycle of therapy (or have experienced a qualifying toxicity prior to the end of the first cycle) will be evaluable for the safety lead-in. Qualifying toxicities will be defined in the first cycle only. Patients must have completed twice-daily sorafenib dosing for at least 21 out of the first 28 days to be considered to have had sufficient exposure to the regimen for qualifying toxicity evaluation. Patients who are not evaluable for the qualifying toxicity assessment for the safety lead-in will be replaced.

Evaluable for qualifying toxicities for the early stopping rule after the safety lead-in. Patients who have initiated the first cycle of therapy will be considered evaluable for the early stopping rule. Qualifying toxicities will be defined in the first cycle only. Patients who are not evaluable for the qualifying toxicity assessment for the early stopping rule will not be replaced unless they were included in the safety-lead in.

Evaluable for objective response. Patients who have been treated with the combination of twice-daily sorafenib and valproic acid for a minimum of 28 days, and have had their disease re-evaluated, will be considered evaluable for response. These patients will have their response classified according to the definitions stated below. Patients who do not complete study dosing for at least 28 days, or those who do not have their disease re-evaluated following initiation of the combination of sorafenib and valproic acid, will be replaced to ensure that a sufficient number of patients will be available for response evaluation.

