Once the dose for expansion to the full cohort is identified, then an early sequential safety stopping rule which is based on the occurrence rate of qualifying grade 3 or greater toxicities is provided to monitor safety for any toxicities in the expansion. The safety lead-in rule is designed for a "3+3" study and is used to enhance safety analysis for the first 6 qualifying toxicity-evaluable patients on the study, whereas the sequential stopping rule for subsequent enrollment has considered the variability of toxicity rate by confidence intervals based on observed data and scenarios where unacceptable toxicity could occur prior to study suspension. More details on the clinical rationale are in Section [1.7](#). Details on the safety lead-in and safety stopping rule are in Section [13.6](#).

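### Some drug-related events below grade 3 end sorafenib permanently under Table 1 but do not count in the safety lead-in, and a lead-in patient stopped early for one is replaced

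*Combined protocol and SAP*

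**What the plan says.** **What counts.** Section 6.4.2 sets one definition for the lead-in and the stopping rule: "Qualifying toxicities are defined as any of the following that are possibly, probably, or definitely related to drug therapy". The only criterion is grade 3 or higher, with a list of exceptions. Section 13.1 repeats the floor for the stopping rule, which is "based on the occurrence rate of qualifying grade 3 or greater toxicities". Nothing is counted because it ends a study drug.

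**What ends sorafenib.** Table 1 in Section 7.1.1 orders permanent discontinuation for several events that start below grade 3:

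- acute coronary syndrome or myocardial infarction, from grade 2;
- hemorrhage that needs medical intervention, from grade 2;
- grade 1 or higher "Alkaline phosphatase in the absence of known bone pathology with grade" 2 or higher bilirubin increase.

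The same instruction applies to AST or ALT above 3 times ULN with bilirubin above 2 times ULN, and to gastrointestinal perforation. Table 1 gives no grade for either.

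**Who is evaluable.** Under Section 10.1 a lead-in patient must complete cycle 1 or have a qualifying toxicity, and exposure is sufficient only with twice-daily sorafenib on at least 21 of the first 28 days. "Patients who are not evaluable for the qualifying toxicity assessment for the safety lead-in will be replaced". For the later stopping rule, anyone who starts cycle 1 is evaluable.

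**The limits.** The lead-in passes if fewer than 2 of 6 evaluable patients have a qualifying toxicity (Table 16). The stopping rule (Section 13.6.2) uses m events in n patients, set against a 35% acceptable rate for grade 3 or greater toxicity.

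**The concern.** Section 13.1 says the lead-in is there to protect against interaction toxicity among the three drugs. A drug-related grade 2 hemorrhage that ends sorafenib on day 10 does not register in that check: the patient has no qualifying toxicity and too few dosing days, so another patient takes the place. By contrast, a related grade 3 acneiform rash is not on the exceptions list and does count, although Table 1 lets sorafenib restart one dose level lower. The lead-in can therefore find a dose safe for expansion after losing from its count some drug-related events that ended sorafenib for good.

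Expedited reporting does not fill the gap. Table 5 sends unanticipated problems and qualifying toxicities to the DSMC, but its SAE column lists no DSMC report. A related event below grade 3 that is serious but not an unanticipated problem reaches neither formal rule nor the two-business-day DSMC report.

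**Working it through.** **1. The plan's own figures.** The boundaries in 13.6.2 are the smallest m for which the lower two-sided 95% Wald limit exceeds 0.35, that is m/n − 1.96·√[(m/n)(1 − m/n)/n] > 0.35.

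- n = 7, m = 4: 0.571 − 1.96 × 0.187 = 0.205, not above 0.35.
- n = 7, m = 5: 0.714 − 1.96 × 0.171 = 0.380, above 0.35, so 5/7.

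This formula reproduces the stated boundary at all 60 values of n from 7 to 66. The arithmetic is sound; the question is which events enter m.

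**2. Following one patient.** Take a related event below grade 3 that Table 1 makes a permanent stop, in a patient with no qualifying toxicity.

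| When | Result under 6.4.2 and 10.1 |
|---|---|
| Lead-in, before 21 dosing days | Non-evaluable and replaced; in neither numerator nor denominator |
| Lead-in, after 21 dosing days | Not settled: exposure is met, but cycle 1 must also be completed, and Section 7 allows treatment to continue without sorafenib. Either replaced or counted event-free |
| After the lead-in | Adds 1 to n and 0 to m |

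**3. Size for the lead-in.** Let c be the per-patient rate of counted toxicity and q the rate in cycle 1 of an uncounted permanent stop without a qualifying toxicity. The documents give neither, so c = 15% or 20% and q = 1%, 5% or 10% are assumptions.

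- P(pass) = (1 − p)^6 + 6p(1 − p)^5.
- As written, p = c/(1 − q) if these patients are replaced, and p = c if they count as event-free.
- With the events counted, p = c + q.

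Example, c = 20% and q = 10%. Counted, p = 0.30: 0.118 + 0.303 = 0.420. Replaced, p = 0.20/0.90 = 0.222: 0.601. Event-free, p = 0.20: 0.262 + 0.393 = 0.655.

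| c | q | As written, replaced | As written, event-free | Counted | Difference (points) |
|---|---|---|---|---|---|
| 15% | 1% | 0.773 | 0.776 | 0.753 | 2.0 to 2.4 |
| 15% | 5% | 0.758 | 0.776 | 0.655 | 10.2 to 12.1 |
| 15% | 10% | 0.737 | 0.776 | 0.534 | 20.3 to 24.2 |
| 20% | 1% | 0.650 | 0.655 | 0.631 | 2.0 to 2.5 |
| 20% | 5% | 0.630 | 0.655 | 0.534 | 9.6 to 12.1 |
| 20% | 10% | 0.601 | 0.655 | 0.420 | 18.1 to 23.5 |

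Replacement, which the early-stop path requires, gives the smaller difference in each row.

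**4. Size for the stopping rule.** Exact recursion over the m/n table, given a passed lead-in, gives the chance of reaching a boundary by n = 66. At c = 20% it is 0.000 as written, and 0.000 or 0.004 with the events counted at q = 5% or 10%. At c = 35% it is 0.025 as written, and 0.108 or 0.305 with them counted.

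**The case against.** **The two sections do different jobs.** Table 1 manages one patient and 6.4.2 counts across patients. Section 7 keeps them apart by saying that a qualifying toxicity need not end treatment. This stands: both sections can be followed at once, so this is a gap in the count and not a strict contradiction. It does not excuse removing the patient from the lead-in altogether.

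**Table 1 is not all about attribution.** The cardiac, perforation and hemorrhage rows do not ask whether the drug caused the event. This also stands, and the point is confined to events judged related.

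**The rates are unsupported.** The prior-study summaries in Section 1.7 name no infarction, perforation or hemorrhage, although they mainly report grade 3-4 events. At 1% the effect is small.

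**Other oversight exists.** All AEs are recorded, the study team meets at least monthly, and 13.6.2 disclaims that an unreached boundary shows safety. True, but none of this feeds the lead-in count.

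**Stronger readings the documents do not support.**

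- A reader might infer that these events never count. At grade 3 or higher they do, if related and not excepted.
- A reader might list the AST/ALT-with-bilirubin rule and perforation as certain cases. Both depend on CTCAE cut-offs that the documents do not reproduce, so they are only possible further cases.
- A reader might conclude that a stop after day 21 always counts as event-free. Section 10.1 also requires a completed first cycle.
- A reader might say that the lead-in passes more often than its stated standard implies. The stated standard is grade 3 or higher; the differences above are against a broader count.

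**Conclusion.** The gap is real, and it matters most in the lead-in. The firm cases, graded in Table 1 itself, are grade 2 acute coronary syndrome or infarction, grade 2 hemorrhage needing intervention, and grade 1-2 alkaline phosphatase with grade 2 bilirubin, each when drug-related. Sections 6.4.2 and 10.1 together take such a patient out of the lead-in when sorafenib stops early.

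The size cannot be fixed from the documents. With counted toxicity assumed at 15-20%, the difference in lead-in pass probability is about 2 points at a 1% event rate, 10-12 at 5% and 18-24 at 10%. These figures are illustrative; the textual finding does not depend on them.

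For the stopping rule the effect is negligible at those rates. Near 35% it would be large, but there a broader m would no longer test the rate the benchmark describes. The lead-in limit of fewer than 2 of 6 does not derive from 35%, so that difficulty does not apply to it. This is a cheap improvement to the definition; the stopping-rule arithmetic is not at fault.

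**What to change.** **Lead-in.** Reconcile 6.4.2, Table 1 and 10.1 with one sentence: a related event for which Table 1 requires permanent sorafenib discontinuation counts in the lead-in whatever its grade, and the patient is evaluable and not replaced.

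**Stopping rule.** Choose one of two routes. Either keep the grade 3 or higher definition for m/n and report these events to the DSMC beside it, or first confirm that the 35% benchmark still applies to the wider definition before adding them to m.

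**Cost.** One sentence for the lead-in, with no extra visits or tests. The downside is a somewhat higher chance of a lead-in hold, which under 13.6.1 means a protocol amendment and 6 further patients. The DSMC route adds a short listing. The change concerns only what is counted and reported, not when any drug is stopped.
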